7 TRIAL PROCEDURES

See appendix 1 for detailed visit structure and trial procedures.

7.1 Participant Identification and Recruitment

Trial participants will be from inpatient admissions in the Clinical Decisions Unit (CDU) at Glenfield Hospital, University Hospitals of Leicester. This admissions unit admits over 95% of all exacerbations of COPD in Leicestershire (catchment population circa. 1 million) and is the second largest acute hospital trust for hospital admissions in the UK. The unit admits approximately 150 patients per month with an exacerbation of COPD.

Potential participants to the trial will be identified as soon as practically possible when they are admitted to the clinical decisions unit (CDU) at Glenfield Hospital by members of their healthcare team. Following admission onto a medical ward, potential participants will be approached by a member of their healthcare team and asked if they would like to consider taking part in the study. If the patient is willing to consider participating in the trial, they will be approached by a member of the research team for further information and consent. On many occasions the healthcare team will also be members of the research team.

7.1.1 Screening

Potential participants will be required to meet a number of eligibility criteria before consent. All potential patients who are screened will have their pseudonymised data (initials and year of birth) added to the screening log and participants will then be assessed for eligibility as per inclusion/exclusion criteria from their patient notes. Eligibility will be confirmed by a physician. If eligible, participants will be approached and asked if they wish to take part in the trial. Once Informed Consent has been given participants will then be randomised into the trial via the web-based randomisation system. The screening log will be maintained by trial staff within the Investigator Site File (ISF). Participants who are deemed not to be eligible or who decline to take part in the trial will be screen failed and their screening log entry identified as screening failure along with the details of their ineligibility/declined invitation. Otherwise, details pertaining to the randomisation (date of consent, randomisation and trial ID) will be completed for all participants who are randomised.

7.1.2 Payment

Participants will be reimbursed for travel expenses at the usual NHS Trust rate (up to a maximum of £50 per visit) payable on production of original receipts at all trial visits. Participants will not receive any additional payment for taking part in the trial.

7.2 Informed Consent

Written versions of the participant information sheet and consent form will be presented to participants detailing the exact nature of the trial: what it will involve for the participant; the implication and constraints of the protocol; the potential side effects and any risks involved in taking part. It will be clearly stated that the participant is free to withdraw from the trial at any time for any reason, without prejudice to future care, and with no obligation to give the reason for withdrawal.

Due to the nature of the study (acute illness resulting in hospitalisation), the participant can be consented at any point within their inpatient stay, or within one week of discharge. Participants will be given time to consider the information and have the opportunity to question the researcher, or other independent parties, to decide whether they will participate in the trial. Written informed consent will then be obtained by means of participant dated signature and dated signature of the person who presented and obtained the informed consent, which will contain information that conforms to current data sharing and handling requirements.

The process for obtaining informed consent will be in accordance with the REC guidance, and GCP and any other applicable regulatory requirements, which may be introduced. Trial procedures including baseline assessments will not be undertaken until the informed consent form has been signed and dated by the participant. Should there be any subsequent amendment to the final protocol, which might affect their participation in the trial, then these will be discussed with the participant and, if applicable, continuing consent will be obtained using an amended consent form.

The original signed consent form will be retained at the study site within the Investigator Site File (ISF). One copy will be given to the participant, and a second copy retained in their medical notes.

7.2.1 Additional consent for biological specimens and future research

Additionally, participants will be given the opportunity to consent to access their primary care records (historical and during the trial), as well as to the storage of their biological specimens in a HTA approved bio-bank at the University of Leicester for future ethically approved research. This is optional and participants will be able to opt out of this without affecting their involvement in the trial. Both data and samples will be pseudonymised and may be transferred externally to collaborators with a further materials transfer agreement.

The research team will also seek permission to use participants' postcodes for future research investigating the link between their disease progression and the environmental pollution in the area in which they live. This will involve linking participants' health data outcomes (e.g. exacerbations) with their postcode by members of the University of Leicester. With consent, data will be transferred encrypted from the University Hospitals of Leicester NHS Trust to named individuals at the University of Leicester for analysis.

7.3 Randomisation

The LCTU will supply a web-based randomisation system from a third party (Sealed Envelope Ltd.). Participants will be randomised in a 1:1 ratio to mepolizumab or placebo. The trial team and participants will be blinded to treatment assignment. Randomisation will be stratified on baseline eMRC dyspnoea score (≤ 3 , > 3) and past hospitalisation in the previous 12 months (0, ≥ 1).

Each participant will be given a unique trial ID number at randomisation. Randomisation results will be printed out and signed as confirmation by the unblinded trial personnel performing the randomisation and a copy will be stored securely with the unblinded documentation and presented to pharmacy alongside the prescription.

7.3.1 Method of implementing the randomisation/allocation sequence

Once the participant has provided written consent to the trial and a physician has confirmed eligibility, randomisation will be performed. Unblinded personnel (authorised and trained) will enter data pertaining to consent, eligibility, pseudonymised identification and stratification onto the randomisation CRF. This data is required to be input into the online randomisation system in order to allocate the participant to a treatment arm. The randomisation system will generate a unique trial ID and determine allocation to either mepolizumab or placebo. The data recorded as part of randomisation will be held by the Sealed Envelope system with restricted access to the trial statistician for safety and DSMC reporting, pharmacy staff, the unblinded trial personnel, and Sponsor only.

7.4 Blinding

Participants, investigators, and all involved in trial conduct, sample analysis, or with any other interest in this trial will remain blind to the randomised treatment assignments until after final analysis is complete. The exception(s) to this are as follows;

- The trial statistician will have access to the web-based randomisation database of all randomised participants in order to prepare the unblinded DSMC to make safety decisions and complete end of trial analyses.
- The Pharmacy team will be unblinded and have responsibility for storing and dispensing IMP and placebo.
- Unblinded trial personnel from the Respiratory BRC will have responsibility for reconstituting the IMP/placebo, where applicable, and dosing the participants.

The IMP, and matched placebo for those dosed from 01 March 2024, will be formulated and packaged by GSK. The placebo treatment will be saline solution for participants dosed before 01 March 2024, with those dosed on or after using a matched placebo from GSK in a pre-filled syringe.

The entire Pharmacy team are unblinded and will take receipt of the IMP and placebo in accordance with their local SOPs and complete the necessary documentation including the accountability logs which will be maintained securely in the trial Pharmacy Site File. They will provide the IMP/placebo to the unblinded trial personnel only. The Unblinded trial personnel will collect and transfer the unprepared IMP/placebo or pre-filled syringes making sure that they are not visible to anyone during transport i.e. transferred in a closed non-transparent bag.

The unblinded trial personnel are designated on the Delegation Log and will be responsible for randomisation and trial drug preparation, reconstitution and administration, which will take place in Glenfield Hospital out of sight of

blinded trial personnel or the participant, with clear warning notices that unblinded IMP is being prepared. All documentation of IMP/placebo preparation, randomisation CRF and prescription containing information about randomisation for each participant, will be kept in a folder in a sealed box or in a secure location not known to the blinded team. A label will be added directly to the syringe containing only the trial ID, initials, a statement that it is 'either drug mepolizumab or placebo within', date, time of preparation, and the initials of the unblinded person preparing it.

This 'blinded label syringe' will be handled by unblinded trial personnel to be administered to the participant on site. There may be slight colour and viscosity differences between the IMP and placebo, which will be mitigated by using an unblinded member of the study team to administer the treatment to the participant.

The treatment allocation will remain blinded to all other trial team members until after database lock.

A DSMC will review the trial data periodically to assess patient safety and will have access to unblinded data as outlined and agreed in the DSMC Charter. Data presented at the DSMC will be prepared by the trial statistician and take the format of an open blinded session followed by a closed unblinded session (as appropriate) to prevent unblinding of the CI, trial manager and the rest of the trial team.

7.5 Emergency Unblinding

The need for code breaking will, if possible, be discussed with the Chief Investigator or designee. The Principal Investigator or delegated Co-Investigator at site will authorise the code break and decide on further management including the need to inform regulatory authorities. Emergency unblinding will be available to the investigator / pharmacist / Sponsor via the web based Sealed Envelope system. The username and password will be tested in advance of the first participant enrolled onto the trial. The Sealed Envelope system will be fully audit traceable until the end of the trial to ensure that blinding has not been compromised. Unblinding will only occur in the case of a medical emergency when the identity of the allocated treatment must be known in order to provide appropriate medical treatment. It is not anticipated that unblinding will be required in this trial as there is no recovery treatment. In the case of a serious adverse event that is deemed at least possibly related to the allocated treatment, the trial treatment will be discontinued. If unblinding occurs, the investigator must record the reason for unblinding, as well as the date and time of the event in the site file and medical notes. Corresponding information will be recorded in the CRF by the investigator. It will also be documented at the end of the trial in any final trial report and/or statistical report. The CI/Investigating team will notify the Sponsor and the Leicester Clinical Trials Unit in writing as soon as possible following the code break, detailing the necessity of the code break. In the case of unblinding an individual participant for safety reasons, appropriate follow-up of safety related events is required until the event(s) has satisfactorily resolved.

Unblinding of all participants will be undertaken by the trial statistician after the last participant has completed their final visit, and the database has been locked.

7.6 Baseline data

Baseline measures will be completed following obtaining of informed consent and randomisation, and prior to first dosing (see section 8.4) as soon as participants are stable and within seven days of discharge. Please see Trial Assessments (section 7.7) below for assessment details.

7.7 Trial assessments

The trial visit schedule and assessments are summarised in Appendix 1. Trial assessments (e.g. Quality of Life/Symptoms Assessments) may be completed remotely by telephone consultation, where possible, and when necessary. Details of all trial visits are presented below.

7.7.1 Visit 1 (Week 0) – Consent & First Dosing

The following procedures will be performed:

- Eligibility checklist from routinely collected data
- Informed consent
- Randomisation
- Baseline measures
 - ECG, Chest x-ray & ABG (completed as part of standard care)
 - Quality of Life /Symptoms Assessments (eMRC X2 for stable and exacerbated states; SGRQ; CAT; WEMWBS; LCADL)
 - Physiological Measures (SPPB; accelerometry; handgrip strength)
 - Inflammatory markers (serum eosinophil count; sputum* eosinophil count)
 - Lung Function[§] (Spirometry data Forced Expiratory Volume in 1 second (FEV1); Forced Vital Capacity (FVC); FEV1 % predicted; FEV1/FVC)
- Baseline exploratory measures
 - Biomarkers (Sputum* inflammatory differential; sputum* sample: microbiome, systemic inflammation; blood sample: Trop I, BNP, FBC, serum, plasma; urine sample)
 - Muscle wasting (quadriceps ultrasound)
 - Immunophenotyping & Microbiology (Blood: RNA, DNA; Sputum*: RNA, Protein multiplex, immunology, microbiology; Urine: lipoproteomics, protein multiplex)
 - Respiratory disease progression assessment: WHO Clinical Progression Scale
- First dosing (see section 8.4).

[§]Results from historical or contemporaneous spirometry testing performed as part of usual care will be collected from hospital and primary care records where available

***Please note that for patients consented to the study during the truncated follow-up phase (July 2023 to December 2023), not all visits listed below will be completed (see section 7.7.5).**

7.7.2 Visits 2-4, 7 & 10 (Weeks 4, 8, 12, 24, 36; each visit \pm 7 days) – Data collection

The following procedures will be performed:

- Review concomitant medication
- Safety & tolerability (AEs, SAEs, Vital signs, Clinical assessments and investigations)
- Urine pregnancy test (if applicable)
- Dosing (see section 8.4)
- Outcome measures
 - Quality of Life /Symptoms Assessments (eMRC; SGRQ; CAT; WEMWBS; LCADL).
 - Physiological Measures (SPPB; accelerometry; handgrip strength)
 - Inflammatory markers (serum eosinophil count; sputum* eosinophil count)
- Exploratory measures
 - Biomarkers (Sputum* inflammatory differential; sputum* sample: microbiome, systemic inflammation; blood sample: Trop I, BNP, FBC, serum, plasma; urine sample)
 - Muscle wasting (quadriceps ultrasound)
 - Immunophenotyping & Microbiology (Blood: RNA; Sputum*: RNA, Protein multiplex, immunology, microbiology; Urine: lipoproteomics, protein multiplex)

7.7.3 Visits 5, 6, 8, 9, 11, 12 (Weeks 16, 20, 28, 32, 40, 44; each visit \pm 7 days) – Dosing only

The following procedures will be performed:

- Review concomitant medication
- Safety & tolerability (AEs; SAEs, Vital signs, Clinical assessments and investigations)
- Urine pregnancy test (if applicable)
- Dosing (see section 8.4).

7.7.4 Visit 13/Final Follow-up (Week 48 ± 7 days) – Final Follow-up (no dosing)

The following procedures will be performed on all participants who completed the trial treatment schedule. Those participants who discontinued treatment prior to visit 12 but remain in the trial will be invited to hospital to attend this final visit.

- Review concomitant medication
- Safety & tolerability (AEs; SAEs, Vital signs, Clinical assessments and investigations)
- Urine pregnancy test (if applicable)
- Outcome measures
 - Quality of Life /Symptoms Assessments (eMRC; SGRO; CAT; WEMWBS; LCADL)
 - Physiological Measures (SPPB; handgrip strength)
 - Inflammatory markers (serum eosinophil count; sputum* eosinophil count)
- Exploratory measures
 - Biomarkers (Sputum* inflammatory differential; sputum* sample: microbiome, systemic inflammation; blood sample: Trop I, BNP, FBC, serum, plasma; urine sample)
 - Muscle wasting (quadriceps ultrasound)
 - Immunophenotyping & Microbiology (Blood: RNA; Sputum*: RNA, Protein multiplex, immunology, microbiology; Urine: lipoproteomics, protein multiplex)

7.7.5 Truncated follow-up

Patients consented from July 2023 will be followed-up on a truncated visit model, with at least 20 weeks of dosing. Where applicable, the Visit 13 Final Follow-up (no dosing) visit will occur 4 weeks ± 7 days from final dosing visit. It will follow the same schedule of assessments as listed in section 7.7.4. Patients will only complete the visits as per the schedule outlined above up until their final dosing visit.

**please note that due to COVID-19 infection risk protocols within the hospital, only spontaneous sputum samples are collected as part of the standard of care*

7.8 Withdrawal criteria

Specified criteria for discontinuation of trial treatment will be for participants that miss more than one dose of the trial treatment or who delay a dose for >4 weeks. The only exception will be when this delay is due to a COPD exacerbation resulting in hospitalisation, in which instance the next dose will be administered at the next due date or as soon as possible afterwards to allow the participant to recover.

Every effort should be made by the research team to keep the participants in the trial. However, participants have the right to withdraw their consent to take part in the trial at any time without having to give a reason and this will not affect their future care. Withdrawal of consent details and reasons (if known) should be recorded on the CRF and in the medical notes.

The investigator may discontinue treatment of a participant at any time if they are not compliant with the trial protocol or to protect the participant's safety and well-being after consultation with the CI. The IMP may also be discontinued in the case of an adverse event which the investigator considers sufficient to jeopardise the safety of the participant. Participants who want to discontinue trial treatment should be encouraged to remain in the trial and

to continue to be followed-up as per the protocol or as per routine care. Participants who discontinue treatment, for whatever reason, will be asked for their consent to continue collecting data, as a minimum this must include data on hospital admissions and deaths for the remainder of the trial (48 weeks) in order to answer the primary outcome. Those declining this will be withdrawn from the trial (thus withdrawing their consent).

Every effort should be made to keep the participant in the trial to collect important efficacy and safety data. Additionally, there are a number of trial assessments (e.g. Quality of Life measures/Symptom Assessments) that may be collected over the telephone if the participant agrees to be contacted. Withdrawals from the trial should be discussed with the CI or their deputy and the Trial Manager. If a participant has withdrawn/discontinued from the trial for any reason, then his/her screening and trial ID number(s) cannot be issued to another participant.

Loss to follow-up will be minimised by diligent liaison with the participant, their medical team and if required the general practitioner. If a participant fails to attend the clinic for trial visit, the research team should contact the participant and re-schedule the missed visit within a week. If the participant cannot be contacted or misses his/her next appointment, the research team should make every effort to contact the participant again by phone and letter. If the participant still cannot be contacted, then he/she will be recorded as 'lost to follow-up'.

A participant will be considered to have completed the trial if they continue to take trial treatment until Visit 12 (Week 44) and attend Visit 13 and/or the Final Follow-up (referred to as Week 48, unless in the truncated follow-up group; for those, this visit is referred to as the Final Follow-up and will not necessarily occur 48 weeks post randomisation). For those on a truncated follow-up, participants will be considered to have completed the trial if they continue to take trial treatment until their final dosing visit (determined by when they are consented and join the study) and attend the Visit 13/Final Follow-up. For the truncated follow-up, this final follow-up will occur 4 weeks \pm 7 days from their final dosing visit.

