7.11 End of trial

This trial will end when the specified number of participants have been recruited, all participants have completed their last follow up visit, data validation has taken place and the database is locked and statistical analysis complete.

Data reported in the final report to REC and MHRA within 12 months of the End of Trial will include the primary and secondary outcomes (see sections 3.3.1 and 3.3.2).

Participants who become lost to Follow Up will be followed-up via their hospital records until 48 weeks to collect information on the number of exacerbations, number of hospitalisations and death. Those consented to truncated follow-up (consented to study from July 2023 onward) will be followed-up via their hospital records until their Final Follow-up visit which will occur 4 weeks \pm 7 days from what would have been their final dosing visit (based on when they are consented to the trial).

The trial will be stopped prematurely if:

- Mandated by the Ethics Committee or the Sponsor
- Mandated by the Medicines and Healthcare products Regulatory Agency (MHRA)
- Following recommendations from the Data Safety Monitoring Committee (DSMC) or otherwise the Trial Steering Committee (TSC) determine the trial should stop
- Funding for the trial ceases

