10 STATISTICS AND DATA ANALYSIS

10.1 Sample size calculation

Readmission rates at 6, 9 and 12 months were 51%, 59% and 64% respectively for patients admitted with a diagnosis of COPD (ICD code: J44) in Leicestershire in 2015. This is in line with national data from the HQIP RCP National COPD audit (2014) which had a readmission rate of 43% at 3 months. In addition, 6% of patients discharged from hospital with an exacerbation of COPD died in the 12 months following admission without hospital readmission.

National UK data from the HQIP funded RCP/BTS National COPD audit (2014; data unpublished) showed 24.9% patients had an eosinophil count of ≥ 300 cells/ μL on admission. In patients with an eosinophil of ≥ 300 cells/ μL on admission ($n=1,587$), 46.1% of patients were readmitted within 3 months of initial hospitalisation, similar to the non-eosinophilic COPD population.

Assuming 65% of patients receiving usual care will have an event by 48 weeks (composite endpoint: hospitalisation or death) and those treated with mepolizumab have a hazard ratio of 0.6, then 226 patients (113 per group) would be required to show a statistical difference power 0.8, $\alpha=0.05$). We have also assumed 5% drop-out (recruited but not receiving first dose) and therefore the final recruitment target of 238 patients.

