10.3.2 Primary outcome analysis

The main approach to primary analyses will be intention-to-treat (ITT), where the ITT population consist of all randomised participants. The primary analysis will fit the Cox proportional hazard model for the primary outcome of the time to re-hospitalisation or death (any cause) as the dependent variable, treatment group as an explanatory factor and baseline MRC dyspnoea score (≤ 3 , > 3) and past hospitalisation in the previous 12 months ($(0, \geq 1)$) (Stratification factors). This analysis will be accompanied by Kaplan-Meier survival curves alongside with log rank test to compare the survival rate between the two groups. A hazard ratio (HR) of the mepolizumab relative to placebo, with their associated 95% confidence interval and p-values will be reported. A p-value ≤ 0.05 will be considered as significant difference. Time until event (re-hospitalisation or death from any cause) will be measured in days from randomisation until re-hospitalisation, death or 12-month follow-up assessment, whichever happens first. Participants with no event (no re-hospitalisation or alive) assessed during follow-up visits will be censored at the last assessment date free from event. Participants who do not complete the 12-month follow-up will be included in the primary analysis; those without a recorded event will be censored. Participants who withdraw from the trial will be censored at the date of withdrawal and participants lost to follow up will be censored at the date last assessment.

Proportional hazard assumption for the Cox proportional hazard model will be checked using the statistical tests and graphical diagnostics based on the Schoenfeld residuals.

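### Protocol 7.8 makes primary-endpoint follow-up opt-in when treatment stops, which risks avoidable loss of admissions and deaths from the intention-to-treat analysis

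*Protocol*

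**What the plan says.** Protocol 7.8: "Participants who discontinue treatment, for whatever reason, will be asked for their consent to continue collecting data". The minimum asked for is admissions and deaths, because these make up the primary outcome, and the period is given in brackets as 48 weeks. Then: "Those declining this will be withdrawn from the trial (thus withdrawing their consent".

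The request covers every stop. Under 7.8 these include stops for more than one missed dose, stops for a dose delayed beyond 4 weeks, and stops decided by the investigator. Protocol 7.5 adds serious adverse events at least possibly related to treatment.

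Protocol 10.3.2, repeated in SAP 6.4.1: "Participants who withdraw from the trial will be censored at the date of withdrawal". SAP 6.4.3 plans no sensitivity analysis of the primary outcome.

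For a different group, Protocol 7.11 says: "Participants who become lost to Follow Up will be followed-up via their hospital records until 48 weeks". Truncated participants are followed in this way to their Final Follow-up date. No consent step is mentioned.

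**The concern.** The primary analysis is by intention to treat on all randomised participants, so it needs admissions and deaths after treatment has stopped as much as before. Section 7.8 makes that follow-up depend on a consent request at the moment of stopping, and the request goes to people who may never have asked to leave. Someone who declines is lost to the primary endpoint from that day.

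Much of this loss looks avoidable. Both endpoint components can be read from hospital records, Protocol 7.11 already uses such records for people who cannot be reached, and Protocol 11.1 says the team will ask for access to secondary care data. If decliners differ in prognosis from those who stay, and differently by arm, or if the drug effect fades after stopping, censoring them moves the hazard ratio. No planned analysis of the primary outcome would show this.

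The 5% drop-out allowance in Protocol 10.1 covers only participants who never receive a first dose, so it does not absorb this loss.

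**Working it through.** **1. The plan's own figure.** Inputs from Protocol 10.1: "Assuming 65% of patients receiving usual care will have an event by 48 weeks"; "those treated with mepolizumab have a hazard ratio of 0.6"; "226 patients (113 per group) would be required"; power 0.8 and alpha 0.05, taken as two-sided.

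- Mepolizumab event proportion: 1 − (1 − 0.65)^0.6 = 0.467. Mean of the two arms: (0.65 + 0.467)/2 = 0.5587.
- Freedman events: (1.960 + 0.842)² × [(1 + 0.6)/(1 − 0.6)]² = 7.85 × 16, which rounds up to 126. N = 126/0.5587 = 225.5, so 226, as stated.
- 226/0.95 = 237.9, so 238, as stated.
- Schoenfeld gives 121 events and N = 217, so the plan appears to have used Freedman.

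**2. Power if decliners are lost.** The documents give neither a stop rate nor a refusal rate. As an assumption, let 10–30% stop by week 48 and 25–50% of them decline. The share withdrawn, w, then runs from 0.10 × 0.25 = 2.5% to 0.30 × 0.50 = 15%. Here w is the share who would be withdrawn by week 48 if no event came first.

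With exponential event hazard λ and withdrawal hazard μ = −ln(1 − w)/48, the event proportion in an arm is λ/(λ + μ) × [1 − exp(−48(λ + μ))]. Power is Φ(√E × (1 − 0.6)/(1 + 0.6) − 1.96) by Freedman, or Φ(√E/2 × |ln 0.6| − 1.96) by Schoenfeld, where E is the expected number of events among 226.

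| w | Expected events | Power, Freedman | Power, Schoenfeld |
|---|---|---|---|
| 0 | 126.3 | 80.2% | 81.9% |
| 5% | 123.5 | 79.4% | 81.0% |
| 10% | 120.7 | 78.4% | 80.1% |
| 15% | 117.9 | 77.5% | 79.2% |
| 20% | 115.0 | 76.4% | 78.2% |

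The cost is about 1 point at 5% and 2 points at 10%.

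**3. Bias, model A: the drug effect persists and withdrawers have twice the hazard afterwards.** Simulated rate ratios with a true hazard ratio of 0.6; events are scaled to 113 per arm.

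| Withdrawn, placebo / mepolizumab | Full follow-up | Censored at withdrawal | Events lost |
|---|---|---|---|
| 10% / 10% | 0.603 | 0.599 | 8.5 |
| 10% / 20% | 0.624 | 0.597 | 12.3 |
| 20% / 10% | 0.585 | 0.599 | 13.0 |

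With no change in hazard after withdrawal (10% / 10%), both ratios are 0.602. Unequal, prognostic withdrawal moves the ratio, and the direction depends on which arm withdraws more.

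**4. Bias, model B: the drug effect is lost on stopping.** On-treatment hazard ratio 0.55; after a stop, both arms take the placebo hazard times 1 or 2. There are 119 per arm and an unadjusted Cox model.

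| Stop (placebo / mepolizumab), decline, hazard multiplier | Full follow-up | Decliners censored |
|---|---|---|
| 10% both, 25%, ×1 | 0.566 | 0.563 |
| 20% both, 50%, ×1 | 0.584 | 0.567 |
| 30% both, 50%, ×2 | 0.619 | 0.585 |
| 15% / 30%, 50%, ×2 | 0.654 | 0.607 |
| 30% / 15%, 50%, ×2 | 0.553 | 0.548 |
| 30% / 10%, 50%, ×2 | 0.539 | 0.544 |

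If stoppers instead keep their own arm's hazard, equal 20% stops give 0.549 either way.

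For scale, the standard error of the log hazard ratio at about 125 events is 2/√125 = 0.179. The 20% / 50% case shifts it by ln(0.584/0.567) = 0.030, or 0.17 of a standard error. The 15% / 30% case shifts it by ln(0.654/0.607) = 0.075, or about 0.42.

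**5. The passages side by side.** For participants lost to follow-up, 7.11 collects records to week 48, but 10.3.2 and SAP 6.4.1 censor them at the last assessment, and 10.8 says last assessment or last seen. Nothing says whether a record check counts as an assessment. Separately, Protocol 8.5 withdraws a participant from the trial after an anaphylactic reaction, with contact at the end if willing, while 7.8 seeks continued collection after any stop.

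**The case against.** The strongest reply is that the plan already treats stopping and withdrawal as different things. Section 7.8 tells staff to encourage stoppers to stay, and allows protocol follow-up, routine-care follow-up or telephone assessment. Section 7.7.4 invites them to the final visit. SAP 4.1.1 refers to an end-of-treatment form, and the SAP disposition table lists trial withdrawal and early treatment stop separately. A person who refuses when asked could also refuse under an opt-out. All of this stands, and it narrows the point to the default that applies when treatment stops. Encouragement does not change that default.

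Two further replies stand. A participant who stops after a first readmission has already had the primary event, so nothing is lost for that endpoint. A delay caused by a hospitalised COPD exacerbation is exempt from the stop rule (7.8, 8.4). The exposure is therefore limited to stops before a first event.

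SAP 6.4.2 plans a per-protocol analysis censored 4 weeks after the last dose. It gives a near on-treatment estimate but does not measure what refusals cost the intention-to-treat one.

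A reader might infer that unreachable participants keep contributing to the primary outcome while reachable stoppers do not. The documents do not support that: records are collected for the former, but the censoring rule stops at their last assessment. Nor does 7.11 say that it rests on the original consent; it is silent on consent, and the consent form was not available for this review.

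**Conclusion.** The point holds as a low-cost improvement to the default. Section 7.8 turns each treatment stop before a first event into a possible loss of primary follow-up, and no planned sensitivity analysis of the primary outcome would reveal the effect.

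The likely size is modest: about 1–2 points of power at 5–10% withdrawn. Bias is small in mild scenarios. It becomes noticeable (for example 0.624 against 0.597, or 0.654 against 0.607) when withdrawal is prognostic and unequal between arms, or when the drug effect is lost after stopping. Every figure rests on assumed stop and refusal rates and on constant hazards.

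Three stronger readings go too far. A treatment stop is not itself a loss; only those who decline are lost. That the loss is related to outcome is plausible but not shown by anything in the documents. And the hazard ratio is not always flattered: both models give cases in the opposite direction.

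**What to change.** - In 7.8, replace the consent request and the sentence that withdraws decliners with wording such as: *Stopping trial treatment does not end trial participation. Admissions and deaths will continue to be collected from hospital records to week 48 or, under truncated follow-up, to the scheduled Final Follow-up date, unless the participant expressly refuses.* This also replaces the bracketed 48 weeks, which does not fit the truncated group.
- First check that the consent form and information sheet cover this, and amend them if not.
- In 10.3.2 and SAP 6.4.1, state that for a participant who stops treatment, only an express refusal of data collection ends primary follow-up early. Report refusals by arm.
- Reconcile 7.11 with 10.3.2, 10.8 and SAP 6.4.1 so that hospital-record follow-up of lost participants counts in the primary analysis.
- Reconcile 8.5 with 7.8 on data collection after an anaphylactic reaction.

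The cost is a wording amendment to the protocol and probably the information sheet, plus matching lines in the SAP. The downside is that participants opt out rather than opt in at treatment stop; their right to refuse is unchanged. The new default protects only stops that occur after it takes effect. For earlier stops, the reporting of refusals and the reconciled censoring rule are what remain useful.
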